### 8.3. Analyses Based on Matched Populations of CINRG and Study 020e

Demographics and baseline characteristics (age, race, ambulation status, corticosteroid use (yes or no), duration of corticosteroid use, corticosteroid type, baseline 6MWD, baseline time to run/walk 10 meters, baseline time to stand from supine, baseline %-predicted FEV1, %-predicted FVC, PEF, NSAA total score) will be summarized descriptively for CINRG and Study 020e

based on each matched population. The summary will be displayed by corticosteroid use (yes vs no) and cumulative steroid use ( $\geq 12$  months vs  $< 12$  months) for baseline ambulatory and non-ambulatory subjects separately. The baseline is defined as the first visit in CINRG data. The comparison to the natural history data (ie, CINRG data) based on matched subjects will be performed in FVC using piece-wise regression models and age to loss of ambulation using Kaplan-Meier method.

Piece-wise regression models will be applied to log FVC in CINRG and study 020e data, separately, using different ages as the changepoint. The most possible changepoint in terms of age will be chosen at the best model fit (ie, AICC value is the maximal). Scatter plots of log FVC and the most fitted piece-wise regression line will be generated for CINRG and study 020e, separately. Comparison between the observed and predicted FVC in study 020e will be performed using repeated measures analysis of variance to account for within-subject correlation, where the predicted values are based on the regression equation estimated by the best fit regression model based on CINRG data.

In study 020e, the loss of ambulation is defined as the disease progression reported as the adverse event or the time to run/walk 10 meters  $> 30$  seconds, whichever occurs earlier. The event age is the one on the AE start date. The subjects who are ambulatory at the end of study will be censored on the last valid timed function tests assessment date. Age on that date will be used in the analysis. In the CINRG data, the age at the earliest report of the non-ambulation or the time to run/walk 10 meters  $> 30$  seconds, whichever earlier, will be picked as the event age. If subjects in CINRG data do not report non-ambulation, the age at the last report of ambulation will be chosen as the censor age. A sensitivity analysis will be performing based on the loss of ambulation defined only by disease progression AE.

For CINRG data only, the observed values will be summarized descriptively for each actual age on 6MWT, time to run/walk 10 meters, time to stand from supine, NSAA total and linear scores, %-predicted FVC, %-predicted FEV1, and PEF by corticosteroid use at baseline (yes or no) and overall based on the matched populations.

NSAA score derivation algorithms in Study 020e will be applied to CINRG data.

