7.21. Spirometry

Spirometry will be conducted in a standardized fashion (see Study Manual for details) and will be performed at Screening/Baseline on Visit 1, Week 24 (Visit 3), Week 48 (Visit 5), Week 72 (Visit 7), and Week 96 (Visit 9), Week 120 (Visit 11), Week 144 (Visit 13- End-of-Treatment/Premature Discontinuation).

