### **8.2. Matched Populations**

To compare CINRG with Study 020e, the matched populations are defined in the following table for different endpoints and analyses.

Endpoint/Analysis	Age (Years) at Study Entry	Age (Years) at Assessment	Steroid Use	Ambulation status	Exclude EXON 51 and 45	Baseline value	Visit Year
Age at loss of ambulation	7-14	Not applicable	Cumulative Steroid use duration at each assessment $\geq 6$ months	Ambulatory at study entry	Yes		Not applicable
Piece-wise regression based on FVC	Not applicable	$\leq 19$	Cumulative Steroid use duration at each assessment $\geq 24$ months	Non-ambulatory at each assessment	Yes	Not applicable	$\geq 2012$
%-predicted FVC	7-15	Not applicable	Not applicable	Non-ambulatory at study entry	Yes		Not applicable
%-predicted FEV1	7-15	Not applicable	Not applicable	Non-ambulatory at study entry	Yes		Not applicable
PEF	7-15	Not applicable	Not applicable	Non-ambulatory at study entry	Yes		Not applicable
6MWT	7-15	Not applicable	Cumulative Steroid use duration at each assessment $\geq 6$ months	Ambulatory at study entry	Yes		Not applicable
time taken to run/walk 10 meters	7-15	Not applicable	Cumulative Steroid use duration at each assessment $\geq 6$ months	Ambulatory at study entry	Yes		Not applicable
time taken to stand from supine	7-15	Not applicable	Cumulative Steroid use duration at each assessment $\geq 6$ months	Ambulatory at study entry	Yes		Not applicable
NSAA	7-15	Not applicable	Cumulative Steroid use duration at each assessment $\geq 6$ months	Ambulatory at study entry	Yes		Not applicable

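### SAP 8.3 provides for repeat FVC measurements only in the final comparison, not in the fit that sets the CINRG line and changepoint; a subject effect there is a cheap improvement

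*SAP*

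**What the plan says.** SAP 8.3 sets out the FVC comparison with CINRG in three steps.

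1. Fit: "Piece-wise regression models will be applied to log FVC in CINRG and study 020e data, separately, using different ages as the changepoint".
2. Changepoint: the age giving the best fit by AICC is kept.
3. Comparison: observed and predicted FVC in 020e are compared "using repeated measures analysis of variance to account for within-subject correlation". The predictions come from the CINRG equation chosen in step 2.

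Steps 1 and 2 name no random effect, covariance structure or clustered standard error. The provision for correlation appears only in step 3.

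The records are repeat assessments. The FVC row of the SAP 8.2 table selects by assessment: age at most 19, at least 24 months of cumulative steroid use, visit year 2012 or later, and "Non-ambulatory at each assessment". Protocol 7.21 schedules spirometry at "Screening/Baseline on Visit 1, Week 24 (Visit 3), Week 48 (Visit 5), Week 72 (Visit 7), and Week 96 (Visit 9), Week 120" and Week 144, so at most 7 tests per boy.

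SAP 1 places the CINRG analysis outside the CSR. SAP 8.1 gives its purpose as assessing long-term treatment benefit.

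**The concern.** The changepoint, both fitted lines and every predicted FVC for 020e come out of steps 1 and 2. A pooled fit gives more weight to boys with more visits and treats stable differences between boys as scatter around the age trend. That costs precision in any case. It also leaves the line unbiased only if the ages at which a boy is observed are unrelated to his FVC level.

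That condition is open to doubt. Protocol 2.1 says patients usually die of heart or lung failure by 15 to 22 years of age, a range that overlaps the analysed window of up to 19 years. If weaker boys leave the registry first, the later part of the CINRG line rests on stronger boys and lies too high. Step 3 cannot correct this, because it takes the CINRG predictions as given.

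**Working it through.** **Nothing to reproduce.** The documents state no sample size, power or precision for this analysis, so the check is by simulation. All inputs below are assumptions unless a section is named.

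**Models compared.** The SAP prints no equation; (a) is the literal reading of its words. For boy i at visit j, with candidate changepoint c:

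- (a) Pooled: log FVC_ij = b0 + b1(age_ij − c) + b2(age_ij − c)+ + e_ij
- (b) With subject effect: the same plus a boy-specific intercept u_i

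Both choose c by highest likelihood over a grid of ages. The parameter count is the same for every c, so within a model this ranks ages as best AICC fit would.

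**Set A.** 60 to 120 CINRG boys, up to 5 yearly visits, truncated at age 19 (SAP 8.2). True c = 13; slope +0.06 per year before and 0.06 − 0.16 = −0.10 after. Visit-error SD 0.10; between-boy SD s = 0.15 to 0.35. Setting aside a small slope variation (SD 0.02), ICC = s²/(s² + 0.10²): 0.0225/0.0325 = 0.69 at s = 0.15 and 0.1225/0.1325 = 0.92 at s = 0.35. A variant used SD 0.20 for both, so ICC 0.5. Exit was either unrelated to FVC or more likely after a low value, with log-odds rising 0.5 or 1.2 per SD.

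**Set B.** 100 boys, yearly visits to age 19, about 4 per boy. True c = 14; slopes before/after of +0.04/−0.10, 0/−0.06 and +0.04/−0.02; ICC 0.64 and 0.90. About 15% exit per visit, either unrelated to FVC or with log-odds rising 0.5 or 1.0 per SD of lower last FVC. One further run (+0.04/−0.10 only) had weaker boys also enter earlier, with and without selective exit.

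| Scenario | Quantity | Pooled (a) | Subject effect (b) |
|---|---|---|---|
| Exit unrelated to FVC | Changepoint RMSE, Set A | 0.16–0.55 y | 0.09–0.20 y |
| Exit unrelated to FVC | The same, repeated at 120 boys | 0.17–0.27 y | 0.08–0.12 y |
| Exit unrelated to FVC | Changepoint SD, Set B | 0.30–1.22 y | 0.21–0.84 y |
| Exit unrelated to FVC | SD of predicted log FVC at 18, Set B | 0.031–0.045 | 0.025–0.032 |
| Weaker boys exit earlier | Line error at 17, Set A (log units) | +0.04 to +0.16 | 0.005 or less |
| Weaker boys exit earlier | Line error at 18, Set B | +4.8% to +16.2% | within ±0.2% |
| Weaker boys exit earlier | Mean changepoint, Set B (truth 14) | 13.54–13.94 | 13.98–14.04 |
| Weaker boys also enter earlier | Line at 12, Set B | 10–18% too low | about 1–4% too low |
| Weaker boys also enter earlier | Line at 18, Set B | 3.5–21% too high | 0.3–2.5% too high |

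**Reading the table.**

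- *Changepoint precision.* Scenario by scenario, the pooled error is 1.3 to 3.7 times larger in Set A and 1.2 to 2.5 times in Set B. For example, at slopes 0/−0.06 and ICC 0.90, 1.13/0.46 = 2.5.
- *Line precision.* Comparing the ends of the Set B ranges, 0.031/0.025 = 1.2 and 0.045/0.032 = 1.4.
- *Line bias under selective exit.* In percent, 100(exp(0.04) − 1) = 4.1% and 100(exp(0.16) − 1) = 17.4%; in Set B, 100(exp(0.047) − 1) = 4.8% and 100(exp(0.150) − 1) = 16.2%. Together this is about 4 to 17%. With exit unrelated to FVC there was no material line bias.
- *Changepoint bias under selective exit.* 0.06 years or less in Set A, where the slope change is steep. In Set B, 14 − 13.94 = 0.06 to 14 − 13.54 = 0.46 years, the larger values coming with shallower slope changes.

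**The case against.** **The SAP is silent, not wrong.** A reader might infer that SAP 8.3 specifies an independence model. It does not: it gives no equation or fitting procedure, lists MMRM among its abbreviations without attaching it to an analysis, and Protocol 10.5.7 allows repeated-measure analysis of pulmonary function. This stands as a limit. The contrast with step 3 still makes pooling the natural reading, and two programmers could reach different changepoints from the same text.

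**The bias needs an exit mechanism that no document describes.** This also stands. Protocol 2.1 makes selective exit plausible but gives no rate. The stronger Set A rule implies leaving after 23% of visits at an average value, 50% at one SD below and 77% at two SD below, which is severe. With log-odds of 0.5 per SD, the line error at 17 was 0.04 to 0.09.

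**Stronger readings a reader might draw.**

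- *Inflated false claims of benefit.* Under the severe exit rule, with 40 boys in 020e and no true difference, step 3 rejected in 25 to 44% of data sets after a pooled fit. That result needs the severe rule, and in a rerun of it every such rejection placed 020e below the CINRG line. Without selective exit, both fits gave 7 to 12%.
- *Confidence intervals for the CINRG line that are too narrow.* SAP 8.3 plans plots, a fitted line and point predictions, but no interval for the line. Carrying the line's sampling error into step 3 is a separate matter.
- *A badly biased changepoint.* The bias was small, as shown above.

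**Weight.** The study's primary objective is safety, there is no formal hypothesis (SAP 3.4), and the study was stopped early (SAP 5.2 and 7), so 7 tests is a scheduled ceiling. This supports a modest label.

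**Conclusion.** The point holds as a cheap improvement. Read as written, SAP 8.3 fits the FVC line and picks its changepoint without using the fact that visits are grouped within boys.

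The loss of precision does not depend on selective exit: changepoint error was about 1.2 to 3.7 times larger, and the CINRG line was also less precise. Line bias is conditional. It is about 4 to 17% too high at ages 17 to 18 if weaker boys leave CINRG earlier, depending on the strength of that link and the between-boy spread. That works against ataluren at those ages. Earlier entry of weaker boys pushes the line down at younger ages, which would favour it. The documents cannot settle the net direction.

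All sizes rest on the assumed slopes, ICC, registry size, visit pattern and exit rules.

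**What to change.** In SAP 8.3, replace the fitting sentence with wording such as: *Piece-wise linear mixed models for log FVC, with a random intercept for subject (and a random age slope if it converges), will be fitted to CINRG and to study 020e separately by maximum likelihood. The changepoint age will be chosen by comparing these fits. Predicted values will come from the fixed effects of the chosen CINRG model. The pooled fit will be shown as a sensitivity analysis.*

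Maximum likelihood rather than REML is needed because the fixed-effect columns change with the candidate age.

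The cost is a few lines of SAP text and a change of procedure in the program, with no new data. There are two limits. The random slope may not converge in a small non-ambulatory subset, in which case the random intercept is used alone. And a random intercept does not fully correct entry that depends on FVC (the table shows 1 to 4% left at age 12), nor exit that depends on unobserved FVC.

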10.3. General Statistical Considerations

By-patient listings will be created for each CRF module. Summary tables for continuous variables will contain the following statistics: n, mean, standard deviation, standard error, 95% confidence intervals (CIs) on the mean, median, minimum, and maximum. Summary tables for categorical variables will include N, n, percentage, and 95% CIs on the percentage. Where applicable, the summary data (mean, standard error) will be presented in graphical form of against time of visit.

Unless otherwise specified, all analyses will be 2-sided at the 0.05 level of significance.

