## 1. OVERVIEW

This statistical analysis plan (SAP) details the statistical methods to be used in the analyses and presentation of the data collected in Study PTC124-GD-020e-DMD, also referred to as Study 020e. Preparation of this SAP incorporates statistical design elements present in the protocol amendment version 2.0 (dated 18 November 2015). Details are documented in sections 1-7.

In addition to the protocol defined analyses, a natural history control using the Cooperative International Neuromuscular Research Group (CINRG) will be utilized in order to help to better understand the long-term ataluren data. Although the planned analysis will not be included in the CSR it will be presented in Section 8 for completeness.

Where conflicts exist between this SAP and the study protocols, the information contained in this SAP supersedes the protocol.

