## **8. CINRG DATA**

### **8.1. Overview of CINRG Data**

CINRG is a natural history registry database which collects DMD data using consortium of medical and scientific investigators from academic and research centers on neuromuscular disease. Demographics and baseline characteristics, corticosteroids medication use (and type), efficacy endpoints including 6MWT, time taken to stand from supine, time taken to run/walk 10 meters, NSAA, spirometry, and EK will be analyzed. Other endpoints collected by CINRG but not in Study 020e will not be included into this analysis plan. The CINRG natural history control (data transferred on November 18, 2016) will be compared to ataluren's efficacy data to assess the ataluren's long-term treatment benefit.

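### SAP 8.3 picks the FVC changepoint by maximal AICC, the reverse of best fit, and then compares Study 020e with CINRG predictions as if they carried no error

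*SAP*

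**What the plan says.** SAP 8.1 gives the purpose of the natural-history data: they "will be compared to ataluren's efficacy data to assess the ataluren's long-term treatment benefit". SAP 8.3 then names two comparisons, age at loss of ambulation and FVC. For FVC the steps are:

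- Fitting: "Piece-wise regression models will be applied to log FVC in CINRG and study 020e data, separately, using different ages as the changepoint".
- Choice of changepoint: "The most possible changepoint in terms of age will be chosen at the best model fit (ie, AICC value is the maximal". AICC is not defined and no candidate ages are given.
- Test: "Comparison between the observed and predicted FVC in study 020e will be performed using repeated measures analysis of variance to account for within-subject correlation".
- Origin of the predictions: the fitted CINRG equation supplies them as point values, and no standard error is attached to them.

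The matched population is the row "Piece-wise regression based on FVC" in SAP 8.2. It caps age at assessment at 19, sets no entry-age limit, and requires at least 24 months of cumulative steroid use, non-ambulatory status at each assessment, exclusion of exons 45 and 51, and a visit year of 2012 or later.

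SAP 8.3 sets no significance level. Protocol 10.3 has a general one: "Unless otherwise specified, all analyses will be 2-sided at the 0.05 level of significance". SAP 1 limits the standing of the work: "Although the planned analysis will not be included in the CSR it will be presented in Section 8 for completeness".

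**The concern.** Three things are wrong or unclear.

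1. The changepoint sentence contradicts itself. Best fit and maximal AICC point in opposite directions unless AICC is sign-reversed, which the SAP does not say. A program that follows the stated criterion draws the wrong CINRG curve, and every predicted value comes from that curve.
2. Whichever changepoint is used, the CINRG equation is itself an estimate. Nothing in 8.3 carries its uncertainty, or that of the changepoint search, into the comparison.
3. The model is for log FVC but the comparison is worded as FVC, so its scale is undefined. This is an ambiguity, not a demonstrated bias.

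Study 020e has no control arm, so a difference found here could be read as a drug effect. Standard errors that are too small let a chance difference pass as benefit or harm.

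**Working it through.** The plan gives no sample size, slope, SD or AICC value for this analysis, so there is no figure to reproduce. Directions below follow from the text; sizes rest on stated assumptions.

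**Sign of the criterion.** AICC = −2 log L + 2k + 2k(k+1)/(n−k−1). Candidate changepoints fitted to the same data share n and k, so the penalty is constant. Maximal AICC is then the lowest likelihood.

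**Effect of following it literally (simulation).** Assumed: true changepoint 14 years; candidates 10–18; 60 CINRG boys with 3 yearly visits at ages 8–19; 60 boys in 020e; between-boy SD 0.25 and residual SD 0.08 on log FVC; five pairs of before/after slopes, from +0.08/−0.08 to −0.02/−0.10 per year; no drug effect; 1,000 runs per pair.

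- The maximal rule chose an end of the age grid in 82–99% of runs and came within 1 year of the truth in 0.1–4.5%. The minimal rule came within 1 year in 71–96%.
- Mean observed minus predicted FVC under the maximal rule, by age mix in 020e:

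| 020e ages | Bias |
|---|---|
| Same as CINRG | −0.1% to +0.1% |
| 8–14 | −1.0% to −1.8% |
| 11–16 | +4.7% to +10.1% |
| 14–19 | −2.1% to −4.2% |

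Under the minimal rule it stayed within 0.5% throughout. The bias therefore needs both the literal rule and different age mixes, and its sign depends on the mix.

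**Omitted variance, with the rule already corrected.** Let s² be the between-boy variance of the mean difference, similar in both cohorts, with similar ages.

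- As planned: Var = s²/n₀₂₀ₑ.
- With CINRG error: Var ≈ s²/n₀₂₀ₑ + s²/n_CINRG.
- With r = n₀₂₀ₑ/n_CINRG, the planned SE is 1/√(1+r) of the true SE, and the true two-sided level is 2[1 − Φ(1.96/√(1+r))].

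| r | Planned SE / true SE | True level of a nominal 5% test |
|---|---|---|
| 0.1 | 0.95 | 6.2% |
| 0.25 | 0.89 | 8.0% |
| 0.5 | 0.82 | 11.0% |
| 1 | 0.71 | 16.6% |
| 2 | 0.58 | 25.8% |

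As an example, r = 1 gives 1.96/√2 = 1.386, hence 16.6%.

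**Simulation check.** This used the minimal rule, a one-sample t-test on each boy's mean log difference, slopes +0.04/−0.04 and 0/−0.08, and 3,000 runs each. With matching ages, the levels at r = 0.25, 0.5, 1 and 2 were about 7–8%, 11%, 17–18% and 25%. With 020e aged 8–14 against CINRG aged 8–19 they were 10–11%, 15–16%, 24–25% and 36–37%. With CINRG aged 10–19, closer to a non-ambulatory group, they were about 5–7% at r = 0.1, 7–9% at 0.25, 16–20% at 1 and 26–31% at 2.

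**Does the remedy work?** Resampling boys in both cohorts and repeating the changepoint search (400 runs, 99 resamples each) gave 4.0–7.0% in all 12 scenarios tried.

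**The case against.** The best defence has four parts.

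- **The AICC wording is a slip.** The same paragraph refers repeatedly to the best or most closely fitting model, including where it defines the predicted values. A sensible programmer would minimise, and the planned scatter plots might expose a bad line. This stands as a reason to expect correction in practice. It leaves the written criterion wrong, and no other section repairs it.
- **The age mixes may be close.** SAP 8.2 requires both cohorts to be non-ambulatory with long steroid use. Protocol 2.1 puts most boys in wheelchairs by 10 to 14 years, so an 020e set aged 8–14 is unlikely and the 24–37% levels tied to it at r = 1 and 2 deserve little weight. With CINRG aged 10–19 and 020e aged 12–19, even the literal rule gave a bias of only +0.7% to +1.1%. This stands, although nothing in 8.2 aligns the ages.
- **CINRG may be much larger.** At r = 0.1 the SE is only about 5% too small, and simulated levels were 4.6–7.3%. The 020e side is a non-ambulatory subset of at most about 220 boys in a study that ended early. This also stands: the size may be small, but the direction does not change.
- **The stakes are modest.** The analysis is outside the CSR, SAP 3.4 states no formal hypothesis, and the primary objective is safety. The simulated t-test is also not the planned ANOVA, whose estimator is unspecified. It does share the feature at issue, which is treating the predictions as fixed.

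**Conclusion.** The concern holds; the text is wrong as written. The AICC direction contradicts the stated aim on the standard definition. The standard errors omit a positive, independent variance component, so they are too small whichever changepoint is used.

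The size cannot be fixed from the documents. If the cohorts have similar ages and variances, a nominal 5% test runs at about 6% when CINRG is ten times larger, about 17% when the cohorts are equal in size, and about 26% when 020e is twice as large. Bias from the literal rule is near zero with matching ages and, in the mixes tried, lay between −4.2% and +10.1%. This should be fixed before the comparison is used to argue for benefit, but it does not touch the safety objective or the CSR.

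**What to change.** In SAP 8.3:

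- Replace maximal with minimal and list the candidate changepoint ages.
- State that observed and predicted values are compared on the log FVC scale, and report the results as ratios.
- Obtain intervals by bootstrapping boys in both cohorts and repeating the changepoint search in every resample. Alternatively, fit one mixed model to log FVC from both cohorts, letting the changepoint differ by cohort, since a later decline could itself be a treatment effect.
- Tabulate age at assessment for both cohorts. The planned summary covers baseline age, which does not describe the assessments that enter this analysis.

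The cost is one word, a few clarifying sentences and modest programming, with no new data. Intervals will widen: in the simulations the standard error grew by a factor of 1.1–1.2 at r = 0.25, 1.4–1.7 at r = 1 and 1.75–2.2 at r = 2.

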At the end of Study 007 (Week 48), the mean change from baseline in 6-minute walk distance (6MWD) was ~30 meters greater in patients treated with the 10, 10, 20 mg/kg dose than in patients treated with placebo, consistent with the 30-meter change specified in the study protocol as being clinically relevant. The improvement among patients treated with the 10, 10, 20 mg/kg dose compared to patients treated with placebo was generally consistent regardless of age, use of corticosteroids, or walking ability at the beginning of the study. There was no difference between the 20, 20, 40 mg/kg-dose and placebo in change in 6MWD over 48 weeks.

Timed function tests of muscle function (stair climbing, stair descending, and walking/running 10 meters) revealed supportive trends for ataluren relative to placebo, as evidenced by less decline over 48 weeks. These changes were clinically relevant at the 10, 10, 20 mg/kg dose. Patient/parent-reported data showed that the frequency of accidental falls over 48 weeks was lower in both ataluren treatment arms relative to placebo. Positive trends favoring ataluren 10, 10, 20 mg/kg vs placebo were also seen for various other measures of physical functioning, including activity and wheelchair use in the community setting, patient-reported physical functioning as measured by the PedsQL, and myometric evaluation of muscle strength.

Mean changes in other secondary outcome measures were generally small; the meaningfulness of these results is unclear given the lack of prior experience in dystrophinopathy and/or other known limitations associated with these evaluations.

These encouraging data led to the conduct of a Phase 3, international, multicenter, randomized, double-blind, placebo-controlled, efficacy and safety study (Study PTC124-GD-020-DMD). This ongoing Phase 3 study includes a treatment period of 48 weeks and an estimated recruitment period of ~18 months at ~50 investigational sites worldwide. The first patient in study PTC124-020-DMD initiated study drug treatment on 10 April 2013.

All patients who successfully complete the Phase 3 double-blind, placebo-controlled study (PTC124-GD-020-DMD) will be eligible for this Phase 3 open-label, extension study (PTC124-GD-020e-DMD). This Phase 3 extension study will evaluate the long-term safety and efficacy of ataluren 10-, 10-, and 20-mg/kg.

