## **7. ANALYSIS CHANGES FROM PROTOCOL**

The supportive analyses on 6-minute walk test have been removed because they are not of the scientific interest any more after the early termination of the study. All paired t-tests have been removed.

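### The CINRG FVC comparison treats a line estimated from CINRG boys as if it were known, so any SE, CI or p-value taken from it is too optimistic

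*SAP*

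**What the plan says.** SAP 8.3 sets out three steps.

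- **Model.** "Piece-wise regression models will be applied to log FVC in CINRG and study 020e data, separately". The changepoint age is picked from the data: it "will be chosen at the best model fit (ie, AICC value is the maximal").
- **Comparison.** "Comparison between the observed and predicted FVC in study 020e will be performed using repeated measures analysis of variance". The stated reason for the repeated-measures form is correlation within a boy.
- **Source of the predictions.** "where the predicted values are based on the regression equation estimated by the best fit regression model based on CINRG data".

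The CINRG line does not come from the whole registry. The FVC piece-wise row of the table in SAP 8.2 requires "Non-ambulatory at each assessment", at least 24 months of cumulative steroid use, no exon 51 or 45 cases, a visit year of 2012 or later, and age at assessment of at most 19. It sets no limit on age at entry. SAP 8.1 dates the data: "The CINRG natural history control (data transferred on November 18, 2016"). The visit-year limit removes only CINRG visits, because the first patient in the parent study "initiated study drug treatment on 10 April 2013".

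SAP 8.1 gives the purpose of the CINRG comparison as judging the drug's benefit over the long term. SAP 1 places it outside the CSR.

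**The concern.** This is a contrast between two cohorts. The predicted values are estimates from one finite set of boys, yet the comparison handles them as fixed numbers. If the CINRG line is too low by chance, it is too low for every 020e boy at once, and 020e looks better than it is. The spread among 020e boys does not reveal that shared error, and no covariance structure fitted to the 020e data can recover it. Nothing in SAP section 8 brings it in: there is no joint model, bootstrap, delta-method term or prediction-error term.

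At stake is how precise the FVC comparison appears. An interval that reflects one cohort's uncertainty would be read as evidence about a difference between two.

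**Working it through.** The plan gives no SE, error rate or subset size for this comparison, so there is no figure to reproduce. The nominal 5% is an assumption: Protocol 10.3 sets a two-sided 0.05 default, but SAP section 8 adds to the protocol analyses and states no level.

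**1. What is omitted.** Let D be the mean over 020e boys of (observed − predicted) log FVC. The two cohorts are different boys, so

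Var(D) = V_020e + V_line.

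Here V_line is the variance of the CINRG-estimated line averaged over the 020e ages. An analysis that holds the predictions fixed reports V_020e at most. Since V_line cannot be negative, the direction does not depend on any assumed figure.

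**2. Size in the simplest case.** Assume a boy-level error term and comparable ages, visits per boy and variance. Then V_line / V_020e = n020e / nCINRG = r, which gives

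true SE / reported SE = sqrt(1 + r)

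actual two-sided error = 2 × [1 − Φ(1.96 / sqrt(1 + r))].

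At r = 0.5: sqrt(1.5) = 1.22, 1.96 / 1.22 = 1.60, and the error is 11.0%.

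| r | SE ratio | Actual error at nominal 5% |
|---|---|---|
| 0.1 | 1.05 | 6.2% |
| 0.25 | 1.12 | 8.0% |
| 0.5 | 1.22 | 11.0% |
| 1 | 1.41 | 16.6% |
| 2 | 1.73 | 25.8% |

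**3. Simulation under no effect.** Assumed: between-boy SD 0.25 and within-boy SD 0.10 on the log scale, up to 4 half-yearly visits, first-assessment ages 10 to 17, changepoint picked by best fit, 1,000 runs per setting.

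| CINRG / 020e boys | r | SE ratio | Error |
|---|---|---|---|
| 300 / 60 | 0.2 | 1.10 | 7.2% |
| 60 / 30 | 0.5 | 1.23 | 9.8% |
| 60 / 60 | 1 | 1.43 | 16.7% |
| 30 / 60 | 2 | 1.77 | 26.4% |

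These agree with the formula. With 020e boys starting at 14 to 17 against CINRG at 10 to 17, the 60 / 60 setting rises to a ratio of 1.70 and an error of 24.1%. Age imbalance therefore enlarges the problem. Adding the variance of the line brought the error to between 4.1% and 5.4% in all eight settings run.

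**4. Changepoint selection.** In a separate simulation (between-boy SD 0.28), selecting the changepoint rather than knowing it moved the error by at most 0.2 points with equal ages and 0.5 points with 020e ages inside the CINRG range. It is a secondary source.

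**5. Error structure.** SAP 8.3 does not say what error term the ANOVA uses. Suppose observed and predicted values are stacked with a single random intercept per boy. The predicted rows carry no boy effect, so the shared intercept cannot absorb it, and a boy's visits are treated as nearly independent. Under the same assumptions as step 4, rejection is about 41% to 43% even when the line is known exactly. So sqrt(1 + r) is not a property of the plan as written. It holds only with a boy-level error term.

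**The case against.** The strongest reply concerns weight. SAP 8.3 promises no SE, CI, p-value or success rule for this comparison, the result is kept out of the CSR, and the study's primary objective is safety. The contrast is non-randomised, so a correct SE still leaves confounding. All of that stands, and it keeps the importance modest. It does not make the error bars right if they are reported.

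A second reply is that a large registry makes the line nearly exact. At r = 0.1 with comparable ages the error is indeed only about 6%. But the filter in SAP 8.2 makes registry size the wrong guide, and the subset size is not stated. The calendar window of under five years does not settle it either, because it says nothing about the number of boys.

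Three stronger readings are tempting and not supported:

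- **Errors of 18% (r = 0.1) or 42% (r = 0.5).** These arise if 020e boys start at 10 to 13 and CINRG boys only at 12 to 17. The documents give no such gap, and SAP 8.2 applies the same row to both cohorts with no lower age limit. With CINRG also starting at 10, the figures are about 8% and 16%.
- **Selective retention of a test.** SAP 7 says "All paired t-tests have been removed", and a reader might infer that this ANOVA was deliberately spared. That section lists changes from the protocol, and this ANOVA was never a protocol analysis.
- **Age left unadjusted.** The row sets no entry-age limit, but age is the regressor in the model. What remains is the risk of extrapolating where the age ranges do not overlap.

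**Conclusion.** The concern holds. As SAP 8.3 is written, the sampling error of the CINRG line is omitted, and any SE, CI or p-value from the comparison is too optimistic. That conclusion needs no assumed numbers.

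The size is not fixed by the documents. Given a boy-level error term and comparable cohorts, it runs from slight at r = 0.1 to substantial at r = 1. It is larger if 020e ages are unbalanced against the CINRG ages or fall outside them, or if the ANOVA has only one random intercept per boy across observed and predicted values. Subset sizes, ages and SDs are all assumptions here.

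This should be corrected before the comparison is reported. It does not affect the safety conclusions.

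**What to change.** In SAP 8.3:

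- State that the comparison is made on the log-FVC scale.
- Take its SE or CI from a bootstrap that resamples whole boys in both cohorts and repeats the CINRG changepoint search in each resample. The search needs an unambiguous criterion, so state the sign convention for AICC: under its usual definition the smallest value, not the largest, marks the best fit.
- Alternatively, fit one joint mixed model of log FVC with a cohort term and boy-level random effects. Note that it assumes a common curve, whereas the plan fits the cohorts separately, and that it conditions on the chosen changepoint.
- Add the number of assessments per cohort and a rule for 020e assessments outside the CINRG age range. Age summaries and n for the matched cohorts are already planned in SAP 8.3 and 5.1.
- Label the result non-randomised and supplementary.

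In a simulated check with equal ages (1,500 runs, 200 resamples, Monte Carlo SE about 0.6 points), the bootstrap brought errors of 7.9% to 24.9% down to 5.7% to 5.9%, and the joint model to 4.3% to 5.1%. The joint model was correct by construction there. With the assumed age gap at r = 0.5, the bootstrap still gave 7.3%, so it does not fully repair extrapolation.

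The cost is SAP wording, modest programming and a wider interval: about 5% wider at r = 0.1, 22% at r = 0.5 and 41% at r = 1 if the cohorts are comparable. No new data are needed.
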